2.3. Benefit/Risk Assessment

2.3.1. Risk Assessment

In CY 5022, treatment emergent adverse events (TEAEs) reported more frequently for the reldesemtiv groups than for the placebo group (with a difference in patient incidence of $> 5\%$) were cystatin C increased, GFR decreased, and fatigue. TEAEs that appeared to increase in frequency with increasing dose included fatigue, nausea, cystatin C increased, GFR decreased, alanine aminotransferase (ALT) increased, and aspartate aminotransferase (AST) increased.

Serum cystatin C was obtained in CY 5022 and used to determine the estimated glomerular filtration rate ($eGFR_{CysC}$) as it was previously recognized that exposure to reldesemtiv resulted in a rise in creatinine; this was attributed to Organic Cation Transporter 2 (OCT2) inhibition. There was a dose dependent decline in $eGFR_{CysC}$ from baseline in CY 5022 and therefore the rise in creatinine observed in prior studies could not be ascribed solely to OCT2 inhibition. Mean $eGFR$ declined to an essentially stable level by 2 weeks of active treatment and tended to recover after 4 weeks off drug. Decline in $eGFR_{CysC}$ was the most common reason for early termination of study drug due to AEs, occurring in 7/457 (1.5%) participants. No patients had significant sequelae related to the decline in $eGFR_{CysC}$ such as requiring dialysis or developing hyperkalemia.

Elevations in ALT or AST greater than $3 \times$ upper limit of normal (ULN) occurred in 25 patients; 24 (7.0%) were assigned reldesemtiv and 1 (0.9%) assigned placebo. Overall, the transaminase elevations appeared to be transient, dose dependent, mild to moderate, and not associated with increase in bilirubin or any clinical manifestations.

A total of 6 patients (none of whom had concurrent elevations in ALT or AST $> 5 \times \text{ULN}$), all on reldesemtiv and 5 in the 450 mg bid group, had a postbaseline total bilirubin value $> 2 \times \text{ULN}$. All elevations were observed within approximately 1 month of starting reldesemtiv dosing and resolved or were normalizing at last contact.

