9.4.1. General Considerations

Summary tables will present descriptive statistics such as number of patients, mean, median, standard deviation, minimum and maximum for continuous variables, and number of patients and the percentage for categorical variables, overall and by treatment in the planned analysis sets. For model-based analysis, least squares means, difference of least squares means between treatments, their standard errors and 95% confidence intervals (CI), and two-sided p-values for the relative statistical inferences will be presented. For survival analyses, time to event will be summarized by median, 95% CIs of median, and 1st and 3rd quartiles. Events and censored data points will be summarized by count and percentage. Hazard ratios between treatments and the corresponding 95% CIs and p-values will also be presented. Baseline is defined as the last available measurement taken before the first dose of randomized study drug received in the placebo control double-blind period unless otherwise specified. Analyses will be conducted by study period including the first 24-week double blind placebo-controlled period, the second 24-week active drug period, and the randomized delayed-start 48 weeks of treatment, and follow-up period.

Listings will include patient ID, demographics, treatment assigned and other relevant items, and sorted by treatment assignment, patient ID and date of assessment.

Unless specified otherwise, efficacy, safety and pharmacokinetics analyses will be performed on the full analysis set, safety analysis set and pharmacokinetics analysis set, respectively. Statistical analysis methods will be detailed in the SAP.

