### 4.2. Definition of Study Drugs

This section describes any study drug: investigational product (IP) (ie, reldesemtiv) or placebo intended to be administered to a trial patient according to the protocol.

Arm Name	Active	Placebo
IP/Product Name	Reldesemtiv	Placebo
Type	Drug	Drug
Dose Formulation	Tablet	Tablet
Unit Dose Strength(s)	150 mg	Matching placebo
Dosage Level(s)	2 tablets twice a day for 600 mg TDD	2 matching placebo tablets twice a day
Route of Administration	Oral	Oral
Use	Experimental	Placebo
IMP and NIMP	IMP	IMP

Arm Name	Active	Placebo
Sourcing	Patheon, Inc. Toronto Regional Operations (TRO) [name]	Patheon, Inc. Toronto Regional Operations (TRO) [name]
Packaging and Labeling	IP will be provided in bottles. Each bottle will be labeled as required per country requirement	Placebo will be provided in bottles. Each bottle will be labeled as required per country requirement

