## **6.6. Baseline Definition**

Unless otherwise specified, baseline is defined as the last available measurement taken prior to administration of the first dose of study drug.

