### **6.7.2. Study Day**

If the date of interest occurs on or after the first dose date, then study day will be calculated as (date of interest – date of first dose) + 1. If the date of interest occurs prior to the first dose date, then study day will be calculated as (date of interest – date of first dose). There is no study day 0.

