### **8.8.2. Exploratory Analyses Evaluating Effect of Reldesemtiv**

To characterize the effect of reldesemtiv, additional comparisons will be conducted based on delayed-start design features.

- The early-start treatment group includes patients who are randomized to receive reldesemtiv. Patients in this group are to receive reldesemtiv during both double-blind, placebo-controlled period and active drug period for a total of 48 weeks.
- The delayed-start treatment group includes patients who are randomized to receive placebo. Patients in this group are to receive placebo during the double-blind, placebo-controlled period for 24 weeks, and then switch to receive reldesemtiv during the active drug period for 24 weeks.

Comparisons listed below will be performed to evaluate treatment differences in 1) change of ALSFRS-R total score from baseline, and 2) combined assessment of change of ALSFRS-R, dependence on assisted ventilation (either invasive or non-invasive), and survival time.

- Compare changes from Week 24 to Week 48 between the early-start and delayed-start treatment groups
- Compare changes from baseline to Week 48 between the early-start and delayed-start treatment groups

- Compare changes from Week 24 to Week 48 versus those from baseline to Week 24 in the delayed-start group

The analysis will include all data collected up to Week 48 (including data from the patients who discontinued the study treatment early but remained in the study and had data being collected). The analysis will also be conducted for patients who were on treatment (ie, excluding data collected after the discontinuation of the study treatment).

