## **9. SAFETY AND TOLERABILITY**

Safety and tolerability analyses will be based on the Safety Analysis Set. Safety data will be analyzed descriptively and tabulated by the early-start and delayed-start treatment groups for the double-blind placebo-controlled period and active drug period).

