In addition, time to ALT, AST or bilirubin elevation since the first dose will be summarized by treatment groups.

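### For delayed-start patients in the active drug period, the safety baseline and the time-to-liver-elevation clock start at the first placebo dose, about 24 weeks before the first reldesemtiv dose

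*SAP*

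**What the plan says.** **Baseline.** SAP 6.6 has one rule, subject to exceptions specified elsewhere: "baseline is defined as the last available measurement taken prior to administration of the first dose of study drug". SAP 4.2 makes clear that placebo counts: "This section describes any study drug: investigational product (IP) (ie, reldesemtiv) or placebo". Protocol 9.4.1 is more explicit: "Baseline is defined as the last available measurement taken before the first dose of randomized study drug received in the placebo control double-blind period".

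**Clock.** SAP 9.5 says "time to ALT, AST or bilirubin elevation since the first dose will be summarized by treatment groups". It does not say first dose of what. SAP 6.7.2 gives the general convention: on or after dosing, "study day will be calculated as (date of interest – date of first dose) + 1".

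**Switch.** SAP 8.8.2 describes the delayed-start group: "Patients in this group are to receive placebo during the double-blind, placebo-controlled period for 24 weeks, and then switch to receive reldesemtiv". Under Protocol 4.1, a patient seen in the morning of Week 24 takes the first active-period dose later that day. A patient seen in the afternoon takes it the next morning.

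**Reporting.** SAP 9 has safety data "tabulated by the early-start and delayed-start treatment groups for the double-blind placebo-controlled period and active drug period". Sections 9.5 to 9.7 call for changes from baseline, laboratory shifts, eGFR decline bands (10%, 25%, 50%), a weight-loss flag at 5% below baseline, and percentages among patients who were normal (or not potentially clinically significant) or missing at baseline. None of these sections defines a later baseline. The SAP measures change from Week 24 only in the efficacy comparisons of 8.8.2.

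**The concern.** Patients randomized to placebo who reach Week 24 form a second cohort with first exposure to reldesemtiv. The laboratory schedule treats them that way: draws at Weeks 26 and 28 repeat the Week 2 and Week 4 draws. The effects of interest come early. In the Phase 2 trial, mean eGFR settled by 2 weeks of active treatment, and for total bilirubin above twice the upper limit of normal the protocol reports: "All elevations were observed within approximately 1 month of starting reldesemtiv dosing".

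The derivation rules do not follow the schedule. If first dose means first placebo dose, an early hepatic signal after the switch appears in the time-to-elevation summary as a late event. If baseline is always Day 1, the delayed-start column of every active-period change table contains whatever happened over 24 weeks on placebo. Abnormalities that arose on placebo and persisted are then counted in the reldesemtiv period.

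**Working it through.** **1. Size of the group.** The plan's own total reproduces. With a difference of 1.8, SD 5.5, two-sided alpha 0.05, 90% power and 2:1 allocation, the placebo number is (1.96 + 1.2816)² × 5.5² × 1.5 / 1.8² = 147.2, rounded up to 148. The evaluable total is 3 × 148 = 444, and 444 / 0.80 = 555. Delayed-start patients randomized: 555 / 3 = 185. If the planned completion rate (444/555 = 80%) applies equally to both arms, 185 × 0.80 = 148 reach the switch.

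**2. Offset of the clock.** Scheduled study day = 7 × week + 1, so Week 24 is day 169, as in SAP Table 15. Offset = days from first placebo dose to first reldesemtiv dose.

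| Week 24 visit | Offset, morning visit | Offset, afternoon visit |
|---|---|---|
| 4 days early | 164 | 165 |
| On schedule | 168 | 169 |
| 4 days late | 172 | 173 |

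The range is 164 to 173 days, or 23.4 to 24.7 weeks. The ±4-day window is from Protocol Table 3.

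**3. Effect on a recorded time** (on-schedule morning visit, offset 168):

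| Elevation found at | Days on reldesemtiv | Days since first study drug | Ratio |
|---|---|---|---|
| Week 26 | 14 | 14 + 168 = 182 | 13 |
| Week 28 | 28 | 28 + 168 = 196 | 7 |
| Week 32 | 56 | 56 + 168 = 224 | 4 |

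**4. Who is reached by the clock error.** Only delayed-start patients whose first elevation comes after the switch. SAP 9.5 does not define elevation for this summary. As an assumption, take the Phase 2 rate of ALT or AST above 3 times the upper limit, 7.0% across all reldesemtiv doses (Protocol 2.3.1). Then 0.07 × 148 = 10.4 and 0.07 × 185 = 13.0, so roughly 10 to 13 patients. That rate covers 12 weeks and includes 450 mg twice daily, which is not used here, so it indicates only the order of magnitude.

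**5. Effect on baseline-dependent results.** Write V0, V24 and Vt for the values at Day 1, Week 24 and a later visit.

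- Reported change: Vt − V0 = (V24 − V0) + (Vt − V24). Only the second term falls in the reldesemtiv period.
- Reported percent decline: 1 − Vt/V0 = 1 − (V24/V0)(Vt/V24). If V24/V0 is 0.90 or less, the patient stays in the 10% eGFR band with no further decline on reldesemtiv.
- Likewise, a patient who has lost 5% of body weight by Week 24 on placebo is flagged again at Weeks 36 and 48 with no further loss.
- The normal-at-baseline denominators select delayed-start patients on values about 24 weeks old at first reldesemtiv exposure.

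**6. Whether period splitting cures this.** SAP 6.1 and SAP 9 divide the observations by period. Neither resets the baseline or the first-dose date.

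**The case against.** **Reading of the clock.** SAP 9.5 says only first dose, and SAP 6.1 has analyses run by period, so a within-period first dose is conceivable. The display specifications are in a separate document. This stands as an ambiguity. But SAP 4.2, 6.6 and 6.7.2 all point to the first dose of study drug, and nothing redefines it. If another meaning is intended, it needs to be written down.

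**Importance.** A reader might infer that the plan hides the onset of hepatic and renal effects, or that the safety endpoint is compromised. The documents do not support either. The safety endpoint is the incidence of adverse and serious adverse events. Events of special interest are summarized from the case report form. Neither depends on the laboratory baseline or this clock. SAP 9.5 also summarizes laboratory measurements at each collection point, and Table 15 gives Weeks 24, 26 and 28 separate windows, so values before and after the switch remain visible. The offset is nearly constant and can be recovered from listed study days.

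**Abnormal-at-entry patients.** Protocol 5.2 excludes bilirubin above the upper limit, and 5.4.1 forbids retesting it. Dropping such patients from the denominator should therefore matter little for bilirubin. ALT and AST are excluded only at 3 times the upper limit or more, so some patients above normal can enter.

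**Choice of baseline.** Day 1 is the randomized baseline, and it keeps the two active-period columns on the same interval. Using Week 24 for one group only would put different intervals side by side. This objection stands and shapes the fix.

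**Conclusion.** The concern holds for one group in one period: delayed-start patients after the switch. For them, any first ALT, AST or bilirubin elevation on reldesemtiv is timed 168 to 169 days late (164 to 173 with visit windows), on the reading of first dose that the SAP's definitions favour. The baseline finding does not depend on that reading. Their active-period changes, shifts, eGFR bands, denominators and weight-loss flag combine placebo-period change with any reldesemtiv effect.

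A reader might infer that all 185 placebo patients receive a wrong time to elevation. They do not. The clock error needs a first elevation after the switch, about 10 to 13 patients under the assumption shown. The baseline mixing is broader and can touch every delayed-start patient with active-period data, about 148 at the planned completion rate. Nor is the Day 1 baseline wrong in itself. It answers a question about total change, and what is missing is a baseline for change since starting reldesemtiv.

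These analyses are descriptive, so alpha, power and sample size do not change. The point still merits correction before database lock, because it alters reported safety results for a first-exposure cohort and is cheap to put right.

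**What to change.** 1. **SAP 9.5, clock.** Time ALT, AST and bilirubin elevation from the first reldesemtiv dose: Day 1 for early-start patients, the first active-period dose for delayed-start patients. Report placebo-period elevations in the delayed-start group separately, timed from first placebo dose. Define elevation for this summary.
2. **SAP 6.6 and 9.5 to 9.7, baseline.** Keep Day 1 as the baseline for the side-by-side tables. Add, for delayed-start patients who take an active-period dose, a pre-reldesemtiv baseline: the last value before that dose, normally from the Week 24 visit. Use it for an additional summary of the first 24 weeks on reldesemtiv (changes, shifts, potentially clinically significant flags, eGFR bands), shown next to early-start Weeks 0 to 24. Footnote that this pairing is not a randomized comparison, since delayed-start patients are those who reached the switch and are 24 weeks further into the trial.
3. **SAP 6.7.5, same-day switch.** That section removes measurements on or after the transition date from the double-blind windows, yet morning-visit patients switch on the Week 24 visit date. State that Week 24 visit values taken before the first active-period dose are pre-switch even when the dates coincide.

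Week 24 laboratory tests, weight, vital signs and ECG are already scheduled, so no new data are needed. The cost is SAP wording, one derived baseline flag and a few extra footnoted descriptive tables.

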## 9.6. Vital Signs

Blood pressure, heart rate, respiratory rate, body weight and oral temperature will be collected at the time points specified in the protocol. For each assessment time point, absolute values and changes from baseline of the vital signs will be summarized.

The count and percentage of patients who had normal or missing values at baseline and Potentially Clinically Significant (PCS) values post baseline will be presented. The PCS criteria are specified in [Table 7](#). For each parameter, the denominator of the percentage will include patients with non-PCS or missing assessments at baseline, and with at least one assessment post baseline. The numerator of the percentage will include patients who had at least one PCS assessment post baseline among the patients that were counted in the denominator. Assessment collected during unscheduled visits or the Follow-up Visit will be included in the summary.

All collected vital signs and assessment time will be listed, and values outside the normal ranges will be flagged.

**Table 7: Criteria of Potentially Clinically Significant (PCS) Vital Signs**

Vital Sign Parameter	Flag	Criteria
Systolic Blood Pressure (mmHg)	High	≥160 mmHg
	Low	≤80 mmHg
Diastolic Blood Pressure (mmHg)	High	≥100 mmHg
	Low	≤ 50 mmHg
Respiration Rate (Breaths per minute)	High	>18 bpm
Respiration Rate (Breaths per minute) (Cont'd)	Low	<8 bpm
Pulse (bpm)	High	≥120 bpm

**Table 7: Criteria of Potentially Clinically Significant (PCS) Vital Signs (Continued)**

Vital Sign Parameter	Flag	Criteria
	Low	≤50 bpm
Weight (kg)	Clinically Significant	≥5% reduction from baseline
Temperature (°C)	High	≥ 38 °C
	Low	< 35 °C

## 9.7. Electrocardiogram

A 12-lead ECG will be obtained at the time points specified in the protocol using an ECG machine that automatically calculates the heart rate and measures PR, QRS, QT, and QTc intervals. Descriptive statistics of absolute value and change from baseline of ECG parameters (PR interval, RR interval, QRS duration, QT interval, QTc interval [Bazett’s and Fridericia’s], Ventricular Heart Rate) at each assessment time point will be presented.

The count and percentage of patients who had normal or missing values at baseline and PCS values post baseline will be presented. ECG parameters are regarded as PCS if the value meets the criterion shown in Table 8. For each parameter, the denominator of the percentage will include patients with non-PCS or missing assessments at baseline, and with at least one assessment post baseline. The numerator of the percentage will include patients who had at least one PCS assessment post baseline among the patients that were counted in the denominator. Assessment collected at an unscheduled visits or the Follow-up Visit will also be included in the summary.

All collected 12-lead ECG parameters, assessment time, ECG findings and interpretations will be listed. PCS ECG values will be flagged.

**Table 8: Criteria of Abnormal and PCS ECG Values**

ECG Variable	Units	Upper Limit of Normal	PCS High Values
QRS Interval	msec	80	≥120
PR Interval	msec	200	≥240
QTcB Interval	msec	Males: 450 Females: 460	>500
QTcF Interval	msec	Males: 450 Females: 460	>500
QT Interval	msec	—	> 500
Ventricular Heart Rate	bpm	—	≤50
			>100

### **9.8. Physical Examination**

Reported abnormal and clinically significant findings in physical examinations will be summarized as Medical History or Adverse Events.

### **9.9. Beck Depression Inventory Fast Screen Version**

The BDI-FS will be assessed at the time points specified in the protocol. Descriptive statistics of the BDI total score will be provided for each assessment time point. The actual assessment date and all reported items will also be listed.

### **9.10. Study Termination Status**

Count and percentage of patients who completed or prematurely discontinued planned study dosing will be presented. Reasons of premature discontinuation will be tabulated. For patients who discontinued prematurely, the date and reason of premature discontinuation will be listed.

## 10. PHARMACOKINETICS

Plasma concentrations of reldesemtiv and its metabolite CK-2127106 at each collection time point will be summarized using descriptive statistics including mean, standard deviation, geometric mean, coefficient of variation, median, and range. Mean plasma concentrations over time will be graphically displayed. PK Parameters, such as  $C_{\text{trough}}$ ,  $C_{\text{max}}$ ,  $T_{\text{max}}$ ,  $AUC_{\text{tau}}$ ,  $AUC_{\text{last}}$  and CL/F (reldesemtiv only) and metabolite ratio, if available, will be summarized. Population PK modeling based on the plasma concentrations of reldesemtiv from this study and previous studies will be conducted; results will be shown in a separate report.

## **12. APPENDIX**

### **12.1. Table of Contents for Data Display Specifications**

Table of contents for data display specifications will be provided in a separate document.

### **12.2. Data Display Specifications**

Data display specifications will be provided in a separate document.

### 12.3. Analysis Windows

Measurements collected during the 24-week double-blind placebo-controlled period will be included only in the analysis windows up to Week 24; measurements collected after patients transition to the active drug period will be included only in the analysis windows after Week 24.

**Table 9: Analysis Windows for ALSFRS-R, FVC (Remote Visits) and DME**

Visit	Scheduled Day	Lower Bound	Upper Bound
Screening a	<1	<1	<1
Day 1	1	1	1
Week 4	29	2	42
Week 8	57	43	70
Week 12	85	71	98
Week 16	113	99	126
Week 20	141	127	154
Week 24	169	155	182
Week 28	197	183	210
Week 32	225	211	238
Week 36	253	239	266
Week 40	281	267	294
Week 44	309	295	322
Week 48	337	323	350
Follow-up	365	351	>351

a Not applicable for FVC (Remote Visits)

**Table 10: Analysis Windows for FVC (in Clinic), Handgrip and Muscle Strength, BDI-FS, Vital Signs, Weight and BMI**

Visit	Scheduled Day	Lower Bound	Upper Bound
Screening	<1	<1	<1
Day 1	1	1	1
Week 4	29	2	56
Week 12	85	57	126
Week 24	169	127	210
Week 36	253	211	294
Week 48	337	295	350
Follow-up	365	351	>351

**Table 11: Analysis Windows for EQ-5D-5L, EQ-VAS and ALSAQ-40**

Visit	Scheduled Day	Lower Bound	Upper Bound
Screening	<1	<1	<1
Day 1	1	1	1
Week 12	85	2	126
Week 24	169	127	210
Week 36	253	211	294
Week 48	337	295	350
Follow-up	365	351	>351

**Table 12: Analysis Windows for Neurological Exam**

Visit	Scheduled Day	Lower Bound	Upper Bound
Screening	<1	<1	<1
Week 24	169	1	266
Follow-up	365	267	>267

**Table 13: Analysis Windows for ECG**

Visit	Scheduled Day	Lower Bound	Upper Bound
Screening	<1	<1	<1
Day 1	1	1	1
Week 24	169	2	252
Week 48	337	253	350
Follow-up	365	351	>351

